4.5.3 Physical and Neurologic Examinations

At the timepoints listed in the schedules of activities (see [REDACTED] and [REDACTED]), a complete physical examination will be performed and should include an evaluation of the head, eyes, ears, nose, throat, neck, and lymph nodes and the cardiovascular, dermatologic, musculoskeletal, respiratory, GI, and neurologic systems. The physical examination will not include pelvic, rectal, or breast examinations.

Limited, symptom-directed physical examinations should be performed as clinically indicated. Changes from baseline abnormalities should be recorded in subject notes. New or worsened clinically significant abnormalities should be recorded as adverse events on the Adverse Event eCRF.

At all timepoints listed in the schedules of activities (see [REDACTED] and [REDACTED]), a neurologic examination will be performed and should include an assessment of mental status, level of consciousness, cranial nerve function, motor function, sensory function, reflexes, coordination, as well as an examination for symptoms of peripheral neuropathy (see [REDACTED] and Section [REDACTED]). Any abnormality identified at baseline should be recorded on the General Medical History and Baseline Conditions eCRF and carefully evaluated in terms of eligibility of the subject for enrollment in this study.

Complete physical and neurologic examinations need to be performed by an examiner with substantial experience in pediatric neurology and experience in examining young children. Based on a child's developmental age, individual capabilities as well as autistic symptoms (e.g., attention span, sensory symptoms, irritability) it is expected that the children will often not be able to be examined in all described evaluation areas.

Body height, weight, and head circumference will be recorded as specified in [REDACTED] and [REDACTED]. *Head circumference will be only measured up to 3 years of age given the availability of CDC published nomograms.* Body mass index (BMI), including age- and sex-specific BMI percentiles relevant for inclusion, will be derived at screening. These anthropometric parameters will be determined according to Centers for Disease Control and Prevention (CDC) BMI Percentile Calculator for Child and Teen (<https://www.cdc.gov/healthyweight/bmi/calculator.html>). Screenshots of this derivation will be kept in the source data.

[REDACTED]

[REDACTED]

[REDACTED]

4.5.4 Vital Signs

Vital signs will include measurement of respiratory rate, pulse rate, and systolic and diastolic blood pressure while the subject is ideally in a seated position, and body temperature. Record abnormalities observed at baseline on the General Medical History and Baseline Conditions eCRF. At subsequent visits, record new or worsened clinically significant abnormalities on the Adverse Event eCRF.

4.5.5 Temperature Measurements

Temperature will be measured at site visits as part of the vital signs assessment (see Section 4.5.4 and [REDACTED] and [REDACTED]).

Body temperature measurements should be taken by the caregiver, at home, once every 2 weeks, at a similar time of the day for the first 30 weeks. Temperature measurements taken at home should be performed using the tympanic thermometer, supplied by the Sponsor, in an indoor environment at room temperature and recorded. Site personnel should train the caregiver on the correct use of the thermometer and the importance of compliance with the procedure. The tympanic thermometer should be returned to site at the end of the subject's study participation.

4.5.6 Laboratory, Biomarker, and Other Biological Samples

Laboratory and biomarker samples will be collected at the timepoints specified in the schedules of activities (see [REDACTED] and [REDACTED]).

Additional blood or urine samples may be obtained at the discretion of the investigator if the results of any test fall outside the reference ranges or clinical symptoms necessitate additional testing to monitor subject safety. When the clinical significance of abnormal laboratory results is considered uncertain, screening laboratory tests may be repeated before treatment assignment to confirm eligibility.

In the event of unexplained abnormal clinically significant laboratory test values, the tests should be repeated immediately and sent to the central laboratory for testing. Abnormal results should be followed until they have returned to the normal range and/or an adequate explanation of the abnormality is found. Results of clinical laboratory testing will be recorded on the eCRF or be received as electronically produced laboratory reports submitted directly from the central laboratory, if applicable.

Samples for the following laboratory tests will be sent to one or several central laboratories for analysis:

- Hematology: WBC count, RBC count, hemoglobin, hematocrit, platelet count, and differential count (neutrophils, eosinophils, basophils, monocytes, lymphocytes, and other cells)

- Serum chemistry panel: sodium, potassium, chloride, bicarbonate, glucose, BUN or urea, creatinine, CPK, total protein, albumin, total and direct bilirubin, ALP, ALT, AST, LDH, total cholesterol, LDL cholesterol, HDL cholesterol, and triglycerides
- Thyroid function and glyated hemoglobin testing: glyated hemoglobin (HbA_{1c}), thyroid-stimulating hormone (TSH), and free thyroxine (also known as T4)

█ [REDACTED]

[REDACTED]

- Coagulation: INR, aPTT, and PT
- Viral serology: HIV
- Urinalysis, including dipstick (pH, specific gravity, glucose, protein, ketones, and blood) and microscopic examination (sediment, RBCs, WBCs, casts, crystals, epithelial cells, bacteria)

Urinalysis will be performed only if feasible for the subject based on their ability to give a urine sample. If there is a clinically significant positive blood or protein result, the urine sample will be sent to the central laboratory for microscopy and culture.

- Plasma samples for PK analysis (see [REDACTED])

Plasma concentrations of balovaptan and its metabolites M3 and M2 (as applicable) will be determined using a specific and validated liquid chromatography-tandem mass spectrometry method. Other balovaptan-derived metabolites in plasma may be investigated as appropriate using an exploratory method.

- Unscheduled visit laboratory assessments

Repeat testing of laboratory parameters listed above or measurement of additional laboratory parameters may be undertaken to interpret any adverse events or abnormal hematologic or chemistry finding. Depending on the adverse event, additional PK samples may also be taken. Decisions regarding unscheduled laboratory assessments will be made by the investigator and in consultation with the Medical Monitor and external experts if necessary.

Samples for the following laboratory tests will be sent to the study site's local laboratory for analysis:

- Capillary blood samples for hematology

[REDACTED]

For all subjects, if venipuncture is not feasible in the opinion of the investigator at specific timepoints noted in the schedules of activities (see [REDACTED] and [REDACTED]), the venous blood hematologic sample can be replaced by capillary blood sampling for analysis of ANC.

- Capillary blood samples for selected serum chemistry (sodium, potassium, creatinine, total and direct bilirubin, ALP, ALT, AST, and CPK)

For all subjects for whom venipuncture appears not to be feasible at that visit in the opinion of the investigator, venipuncture can be replaced by capillary blood sampling.

[REDACTED]

Per the schedules of activities ([REDACTED] and [REDACTED]), the total blood volume taken per individual in this study will not exceed 1% at any single visit or 3% of the total blood volume during a 4-week period. (The total volume of blood is estimated at 80–90 mL/kg body weight.) Please note that unscheduled visits or losses during the maneuver may increase the blood volume. If there is uncertainty with regard to the total blood volume to be collected at any timepoint, the Medical Monitor or designee should be contacted.

If the available blood volume from venous blood sampling is insufficient for all scheduled laboratory tests, the blood sample prioritization below should be followed.

1. PK
2. Hematology
3. [REDACTED]
4. Serum chemistry
5. Coagulation
6. Thyroid function testing
7. Viral serology

For sampling procedures, storage conditions, and shipment instructions, see the laboratory manual.

Biological samples will be destroyed when the final Clinical Study Report has been completed, with the following exceptions:

- Plasma samples collected for PK analysis may be needed for PK assay development and validation; therefore, these samples will be destroyed no later than 5 years after the final Clinical Study Report has been completed.

When a subject is withdrawn from the study, samples collected prior to the date of withdrawal may still be analyzed, unless the subject's parent or legal guardian specifically requests that the samples be destroyed or local laws require destruction of the samples. However, if samples have been tested prior to withdrawal, results from those tests will remain as part of the overall research data.

Data arising from sample analysis will be subject to the confidentiality standards described in Section 8.4.

4.5.7 Palatability Test

Palatability (taste and acceptability) testing of the dispersible tablet formulation of the study drug will include questions directed to the caregiver to capture subjective experiences with the dispersible tablets. Furthermore, the input of the caregiver will also be sought to aid interpretation of the experience or reaction of the subjects.

Palatability assessment will be performed at the timepoint specified in the schedule of activities [REDACTED] after administration of study drug.

4.5.8 Electrocardiograms

At baseline, ECGs will be recorded in triplicate, if feasible. Single ECG recordings will be obtained at specified timepoints, as outlined in the schedules of activities (see [REDACTED] and [REDACTED]), and may be obtained at unscheduled timepoints as indicated.

All ECG recordings must be performed using a standard high-quality, high-fidelity digital electrocardiograph machine equipped with computer-based interval measurements. Lead placement should be as consistent as possible. ECG recordings must be performed after the subject has been resting in a supine position for at least 5 minutes if feasible. All ECGs are to be obtained prior to other procedures scheduled at the same time (e.g., vital sign measurements, blood draws) and should ideally not be obtained within 3 hours after any meal. Circumstances that may induce changes in heart rate, including environmental distractions (e.g., television, radio, conversation), should be avoided during the pre-ECG resting period and during the ECG recording if feasible.

For safety monitoring purposes, the investigator must review, sign, and date all ECG tracings. Paper copies of ECG tracings will be kept as part of the subject's permanent study file at the site. Digital recordings will be stored at a central ECG laboratory. The following parameters will be provided as non-eCRF data: heart rate, RR interval, QRS interval, pulse rate duration, uncorrected QT interval, and QTcF based on the machine readings of the individual ECG tracings or, if considered appropriate by the Sponsor, ECGs may be analyzed at a central laboratory.

If at a particular postdose timepoint the mean QTcF is >500 ms and/or >60 ms longer than the baseline value, another ECG must be recorded, ideally within the next 60 minutes, and ECG monitoring should continue until QTcF has stabilized on two

successive ECGs. The Medical Monitor should be notified. Standard-of-care treatment may be instituted per the discretion of the investigator. If a PK sample is not scheduled for that timepoint, an unscheduled PK sample should be obtained. A decision on study drug discontinuation should be made, as described in Section [REDACTED]. The investigator should also evaluate the subject for potential concurrent pro-arrhythmic risk factors (e.g., electrolyte abnormalities, concomitant medications known to prolong the QT interval, severe bradycardia).

[REDACTED]

[REDACTED]

[REDACTED]

[REDACTED]

- | [REDACTED]
- | [REDACTED]
- | [REDACTED]
- | [REDACTED]
- | [REDACTED]
- | [REDACTED]
- | [REDACTED]
- | [REDACTED]

- | [REDACTED]
- | [REDACTED]
- | [REDACTED]

[REDACTED]

[REDACTED]

[REDACTED]

4.5.10 Requirements for Caregivers

The caregiver must live with the subject or have substantial and sufficient periods of contact with the subject and be willing and able to attend the on-site visits when required. The caregiver must oversee the subject’s adherence with protocol-specified procedures and study drug dosing (see Section 4.3.2), and report on the subject’s status by means of completion of caregiver-reported/completed study assessments.

All disease-specific assessments will take place on site at the clinic. The same caregiver will provide feedback on all informant-based assessments throughout the study as established at baseline, and the same caregiver should accompany the subject to the visits at baseline, Weeks 6, 12, 24, and 54, and early termination. If a caregiver visit cannot be completed as arranged (e.g., the caregiver is delayed in transit), visits should be rescheduled as soon as possible after the original appointment. Caregiver-reported/completed assessments cannot be conducted over the telephone. A change of the reporting caregiver initials will be captured on the eCRF at all assessments.

4.5.11 Clinical Outcome Assessments

Observer-reported outcome (ObsRO) and clinician-reported outcome (ClinRO) instruments will be completed. ObsRO data will be collected through use of the following instruments: Vineland-II, CaGI-C, and CaGI-S. ClinRO data will be collected through use of the following instruments: Vineland-II, ADOS-2, CGI-I, CGI-S, and Columbia-Suicide Severity Rating Scale (C-SSRS). The ADOS-2 will be administered only at screening. The other instruments should be administered as per the schedules of assessments (see [REDACTED] and [REDACTED]) and in the order shown in Table 1.

Table 1 Sequence of Scale Administration

Order	Scale	Respondent(s)	
1	Vineland-II	Caregiver	Qualified rater
2	C-SSRS	Caregiver	Qualified rater
3	CaGI-S	Caregiver	—
4	CaGI-C	Caregiver	—
5	CGI-S	—	Qualified rater
6	CGI-I	—	Qualified rater

CaGI-C = Caregiver-reported Global Impression–Change;
CaGI-S = Caregiver-reported Global Impression–Severity;
CGI-I = Clinical Global Impressions of Improvement; CGI-S = Clinical Global Impressions of Severity; C-SSRS = Columbia-Suicide Severity Rating Schedule; Vineland-II = Vineland™ Adaptive Behavior Scales, Second Edition.

4.5.11.1 Data Collection Methods for Clinical Outcome Assessments

ObsRO instruments will be administered at the clinic at specified timepoints during the study (see schedules of activities in [REDACTED] and [REDACTED]). At the clinic, instruments will be administered before the observer receives any information on disease status, prior to the performance of non-ObsRO assessments, and prior to the administration of study treatment, unless otherwise specified.

ObsRO instruments, translated into the local language as appropriate, will be completed through use of an electronic device provided by the Sponsor. The device will be pre-programmed to enable the appropriate instruments to be administered in the correct order at each specified timepoint. The electronic device and instructions for completing the instruments electronically will be provided by the site staff. A backup device will be provided to each site in the event of device issues. The data will be transmitted to a centralized database maintained by the electronic device vendor. The data will be available for access by appropriate study personnel.

During clinic visits, ObsRO instruments should be administered as outlined below:

- Subjects' health status should not be discussed prior to administration of the instruments.
- Sites must administer the official version of each instrument, as provided by the Sponsor.
- Sites should allow sufficient time for observers to complete the instruments, estimated to be from 0–70 minutes, depending on the visit.
- Sites should administer the instruments in a quiet area with minimal distractions and disruptions.
- Observers should be instructed to answer questions to the best of their ability; there are no right or wrong answers.
- Site staff should not interpret or explain questions but may read questions verbatim upon request.
- Observers should not obtain advice or help from others (e.g., family members or friends) when completing the instruments.

ClinRO instruments will be completed at the clinic at specified timepoints during the study (see the schedules of activities in [REDACTED] and [REDACTED]). ClinRO instruments will be administered after any ObsRO measures and prior to the administration of study treatment. The instruments will be completed through use of an electronic device provided by the Sponsor. Clinicians must complete the official version of each ClinRO instrument, as provided by the Sponsor. The data will be transmitted to a centralized database maintained by the electronic device vendor.

Rater qualification for specific-outcomes assessments, including, but not limited to, the Vineland-II and ADOS-2 will be reviewed per the criteria established by the Sponsor. Only raters confirmed by the vendor to be qualified on those assessments should rate in this study.

If the same qualified rater is not available within the visit window, delaying the visit is preferred to changing the rater. The same rater or clinician will perform the Vineland-II together with the same caregiver throughout the study as established at the baseline visit.

4.5.11.2 Description of Clinical Outcome Assessment Instruments Vineland™-II Adaptive Behavior Scales, Second Edition

The Vineland-II is an instrument that measures communication, daily living skills, socialization, maladaptive behavior (not assessed in this study), and motor skills (Sparrow et al. 2005). The Vineland-II will be administered by a qualified rater at the clinic as a semi-structured interview of the caregiver, during which the rater will ask the caregiver open-ended questions relating to the subject's activities and behavior.

Standardized domain scores will be obtained for the individual domains of Socialization, Communication, Motor Skills and Daily Living Skills. Standardized scores range from 20 to 160 with a mean of 100 and standard deviation of 15. Higher scores indicate better adaptive behavior skills. The Vineland-II 2-DC is calculated as the arithmetic mean of the Socialization standard score and Communication standard score.

The interview will take approximately 45–60 minutes to complete and will be audio recorded.

Autism Diagnostic Observation Schedule, Second Edition

The ADOS-2 is a diagnostic tool used to document the presence of ASD (Lord et al. 2000; Gotham et al. 2007). During a semi-structured evaluation, the individual is observed in a naturalistic social situation and assessed across areas of social communication, imagination, and restricted and/or repetitive behaviors.

The ADOS-2 includes modules for use with different age groups and language levels. The appropriate module of the ADOS-2 will be administered by a certified rater to subjects at the clinic at screening. Scores range from 1 to 10 once the algorithm is applied, with higher scores indicating greater severity of ASD symptoms.

Clinical Global Impression–Improvement

The CGI-I is a single-item, clinician-rated measure, assessing the clinician's impression about changes in the subject's condition, in this case, ASD (not other conditions or comorbidities), compared with baseline.

The CGI-I utilizes a 7-point response scale, ranging from "very much improved" (1) to "very much worse" (7).

Clinicians should make a judgment on any changes from baseline based on the totality of information available to them (e.g., insights from subject and/or caregiver, information captured during the completion of other trial assessments).

The assessment will take up to 5 minutes to complete.

Clinical Global Impression–Severity

The CGI-S is a single-item, clinician-rated measure, assessing the clinician's impression of the severity of a subject's condition, in this case, ASD (not other conditions or comorbidities).

The CGI-S utilizes a 7-point response scale, ranging from "normal, not at all ill" (1) to "among the most extremely ill subjects" (7).

Clinicians should make a judgment on a subject's severity based on the totality of their experience of the population.

The assessment will take up to 5 minutes to complete.

Caregiver Global Impression–Change

The Caregiver Global Impression–Change (CaGI-C) is a 5-item, informant-based measure assessing the caregiver's impression about changes in subject's communication skills, social skills, daily living skills, and overall ASD compared with baseline.

The CaGI-C items utilize a 7-point response scale, ranging from "very much improved" (1) to "very much worse" (7). Each item is scored independently.

There is also an item asking about the importance any of the changes they have observed during the study.

The assessment will take up to 5 minutes to complete.

Caregiver Global Impression–Severity

The Caregiver Global Impression–Severity (CaGI-S) is a 4-item, informant-based measure, assessing the caregiver's impression about the severity of impairment of the subject's communication skills, social skills, daily living skills, and overall ASD during the preceding 7 days.

The CaGI-S items utilize a 5-point response scale, ranging from "no difficulty" (1) to "extreme difficulty" (5). Each item is scored independently.

The assessment will take up to 5 minutes to complete.

Columbia–Suicide Severity Rating Scale

The assessment of suicidality in clinical trials is a requirement for CNS-active molecules requested by health authorities.

The C-SSRS (<http://www.cssrs.columbia.edu>) is a clinician-rated tool recommended by health authorities including the U.S. Food and Drug Administration (FDA) to assess previous suicidality of a subject at screening (C-SSRS screening to be used at screening) as well as any new instances of suicidality during the clinical study (C-SSRS since last visit; to be used at subsequent visits). The C-SSRS incorporates a structured interview to prompt recollection of suicidal ideation, including the intensity of the ideation, behavior, and attempts with actual/potential lethality.

An age-specific version of the C-SSRS will be used for children and this version will be applied in those children being at least 3 years old at baseline or after having turned to an age of 3 years during the study. No suicidality assessment will be performed for children younger than 3 years old.

After completion of the pediatric C-SSRS questionnaire, the investigator will ask the following additional questions relating to the areas of suicidal ideation, suicidal behavior, and self-injurious behavior (verbal or behavioral manifestations):

- Suicidal ideation: Has the child wished he or she were dead or wished he or she could go to sleep and not wake up?
- Suicidal behavior: Has the child made a suicide attempt? Has he or she done anything to harm himself or herself?
- Self-injurious behavior: Has the child engaged in non-suicidal self-injurious behavior?

If the investigator concludes there is a risk for suicidality, the investigator must take care for further evaluation of the risk, which may involve local experts in the field of suicidality.

The assessment will take up to 10 minutes to complete.

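### Children enrolled at age 2 have no suicidality or self-injury assessment before dosing, so a first positive answer after they turn 3 on treatment is hard to distinguish from new behavior on balovaptan

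*Combined protocol and SAP*

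**What the plan says.** The text is in Section 4.5.11.2, under Columbia-Suicide Severity Rating Scale.

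- **Who is assessed.** The pediatric version applies to "those children being at least 3 years old at baseline or after having turned to an age of 3 years during the study". The next sentence reads: "No suicidality assessment will be performed for children younger than 3 years old".
- **Which form.** Two are described. One covers previous suicidality ("C-SSRS screening to be used at screening"). The other covers "any new instances of suicidality during the clinical study" and is given as "C-SSRS since last visit; to be used at subsequent visits".
- **Added questions.** "After completion of the pediatric C-SSRS questionnaire, the investigator will ask the following additional questions", on suicidal ideation, suicidal behavior and self-injury. They include "Has he or she done anything to harm himself or herself" and "Has the child engaged in non-suicidal self-injurious behavior". None states a period.

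Section 3.1 names suicidality as a safety outcome assessment and plans about 3 two-year-olds among 10 subjects, a ratio that may change. Section 4.2 describes a single arm. Treatment is 6 weeks plus an optional 48-week extension.

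**The concern.** Without a control arm, a finding on treatment is read mainly against what was known about the same child before the first dose. Children aged 3 or 4 at screening have a structured reference for suicidality and self-injury. Children aged 2 at screening and at baseline do not. Their series opens on treatment, at whichever visit first follows the third birthday.

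If a caregiver then reports self-injury, the question does not establish whether it began before or after the first dose. A long-standing behavior could be read as a drug effect. A real change could equally be dismissed as long-standing. With 10 subjects, one ambiguous child matters to the safety description, and a missing pre-dose answer can later be rebuilt only from recall.

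**Working it through.** **1. The plan's own figure.** Section 3.1 targets about 2:1 (ages 3–4 to age 2). For 10 subjects: 10 × 2/3 = 6.7, rounded to 7; 10 × 1/3 = 3.3, rounded to 3. This reproduces the stated 7 and 3, so up to 3/10 = 30% of the planned sample could lack the pre-dose assessment.

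**2. Do these children reach age 3 on treatment?** 6 + 48 = 54 weeks = 378 days. A child aged 2 reaches the third birthday within at most 366 days. So every 2-year-old who completes the extension becomes eligible for a first C-SSRS on treatment.

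**3. When?** The documents give no age distribution within the age-2 group. Assume age at Day 1 is uniform over the year from the second to the third birthday. One year is 365.25/7 = 52.18 weeks. The share turning 3 by week w is p = min(1, w/52.18), and the chance that at least one of 3 does so is 1 − (1 − p)³.

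| By week | p | Expected of 3 | Chance of at least one |
|---|---|---|---|
| 6 | 0.115 | 0.34 | 0.31 |
| 12 | 0.230 | 0.69 | 0.54 |
| 24 | 0.460 | 1.38 | 0.84 |
| 54 | 1 | 3 | 1 |

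Because the age ratio may change, the Week 6 chance was also worked out for 2, 3, 4 and 5 two-year-olds: 0.22, 0.31, 0.39 and 0.46. The issue belongs mostly to the extension.

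**4. Children who turn 3 during screening.** On the same uniform assumption applied to age at screening, 4/52.18 = 0.08 to 6/52.18 = 0.12 would turn 3 within a 4- to 6-week screening period. They are 3 at baseline, so they can be assessed before dosing. The 30% is therefore an upper figure.

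**5. Does another assessment supply the reference?**

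- Medical history (Section 4.5.2) is taken for every child but does not name self-injury.
- The neurologic examination (Section 4.5.3) includes mental status, and baseline abnormalities are recorded. The same section expects that many children cannot be examined in every area.
- The Vineland-II (Section 4.5.11.2) omits its maladaptive behavior domain.
- The rules on preexisting conditions and on worsening of ASD (Sections 5.3.5.8 and 5.3.5.9) keep unchanged conditions out of the adverse event record. They work only if the starting point is known, and they do not say how a first positive answer to these questions is classified.
- Historical data (Section 3.3.1) give context. The ASD studies visible in Section 1.2.2 cover ages 5–17 and adults, and no historical series replaces a child's own status before dosing.

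**The case against.** The strongest case against is that the protocol already protects against misattribution. Every child has a history at screening and interval histories later, baseline findings are recorded, and a preexisting condition is an adverse event only if it worsens. That stands in part: an investigator who happens to elicit prior self-injury has somewhere to record it and a rule to apply. Nothing visible requires the question to be asked.

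A reader might go further and infer that the since-last-visit form causes older self-injury to be recorded as newly arising on balovaptan. The documents do not support that, for three reasons.

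- The form for a child whose first C-SSRS falls on treatment is not stated. The since-last-visit form is a literal reading of the text on later visits, and the schedules of activities are redacted in the public copy.
- Non-suicidal self-injury is a separate question outside that form, so the form cannot re-date it. The weakness there is the missing time frame.
- No visible text classes a first positive answer as treatment-emergent. Parts of Sections 5.1 and 6.5 are also redacted, so the absence of a handling rule cannot be shown.

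A reader might also expect a bias of 10 percentage points per misclassified child (1/10). The arithmetic is right, but suicidality is not among the visible endpoints in Section 2.2, and Section 6.5 plans listings and descriptive summaries. No suicidality incidence is visibly planned for that figure to bias.

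Finally, the question on self-harm under suicidal behavior states no intent and can look as if it overlaps with the self-injury question. It directly follows the suicide-attempt question, and the next item is labelled non-suicidal. Adding an intent condition would be a drafting preference, and it is not pressed here.

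**Conclusion.** The concern holds in limited form. The protocol gives children under 3 no suicidality assessment and no self-injury question before dosing, then starts both on treatment once they turn 3, with undated added questions and no opening form named. A first positive answer in such a child may be recorded as new on balovaptan, or be hard to distinguish from it.

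The size is up to about 3 of 10 planned subjects. That upper figure assumes the planned age split, that the 2-year-olds are still under 3 at baseline, and that all of them enter and complete the optional extension. By Week 6 it is about 0.34 of 3 children, assuming uniform ages. How many would have prior self-injury is not given in the documents, so no expected number of ambiguous findings can be stated.

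The primary pharmacokinetic objective is unaffected. This is an inexpensive improvement to safety data that cannot be collected before dosing once the first dose has been given.

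**What to change.** 1. Ask the caregiver of every child, including 2-year-olds, the non-suicidal self-injury question before the first dose and record the answer. It can be separated from the C-SSRS, so the age limit on the C-SSRS can stay.
2. State that, for a child who turns 3 on study, the first visit on or after the third birthday uses the C-SSRS form that captures previous history, with the since-last-visit form only from the following visit. State also which form applies to a child who turns 3 between screening and baseline.
3. Give the added questions a time frame: before the first dose, or since the last visit.
4. In the SAP, flag children with no pre-dose C-SSRS or summarize them separately.

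The cost is protocol and SAP wording, assignment of the electronic form by age at visit, and a few minutes of caregiver time at baseline for about 3 children. One limit remains: the C-SSRS history for these children is still collected on treatment and rests on caregiver recall. Only the self-injury question gains a true pre-dose answer.
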